5.2 Patient Population

All patients presenting to the Johns Hopkins Avon Foundation Breast Center for surgical management of high risk for breast cancer, pre-malignant breast lesions, or breast cancer leading to bilateral mastectomies with reconstruction will be evaluated for participation. Those meeting inclusion criteria and no exclusion criteria may be enrolled into the study.

5.2.1 Inclusion Criteria

Eligible participants must

- Be Female aged 18-100 years.
- Choose bilateral mastectomy followed by bilateral immediate tissue expander breast reconstruction.
- Have no inflammatory breast cancers.
- Be aware of the nature of her malignancy.
- Understand the study purpose, requirements, and risks.
- Be able and willing to give informed consent.

5.2.2 Exclusion Criteria

Participants with the following conditions will be ineligible:

- Any concurrent opioid analgesic use (baseline opioid use must be 0 to be eligible).
- Liver dysfunction and/ or cirrhosis.

- Renal insufficiency, with creatinine greater than 1.5 mg/mL.
- Patients weighing less than 50 Kg.
- Concurrent use of the SSRI antidepressant fluvoxamine (Luvox).

Having a tattoo on the back that is too large to permit PVB injections (as determined by the provider performing the procedure).

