9.5 Data and Safety Monitoring

This is a DSMP Level I study under the SKCCC Data Safety Monitoring Plan. The Clinical Research Office QA Group will perform an audit at the end of the first year and then periodically depending on the rate of accrual and prior audit results. The SKCCC Safety Monitoring Committee will review all trial monitoring and reporting annually. The PI will be responsible for monitoring the study. The study's data will be continuously reviewed to assure its validity. The PI will constantly review the safety reports to confirm that the safety outcomes favor continuation of the study. Additionally, the PI will be responsible for maintaining the clinical protocol, monitoring clinical trial efficacy endpoints, reporting adverse events, assuring that consent is obtained and documented, reporting of unexpected outcomes, and reporting the status of the trial in the continuing renewal report submitted to the IRB and to the trial monitoring review group.

Content of the continuing renewal report at a minimum will include year-to-date and full trial data on: accrual and eligibility, protocol compliance, treatment administration, toxicity and ADR reports, response, survival, regulatory compliance and compliance with prearranged statistical goals. The report will be submitted in a timely manner according to the schedule defined by Johns Hopkins Medicine Institutional Review Board.

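### The renal exclusion in Section 5.2.2 is set at creatinine above 1.5 mg/mL, which is 150 mg/dL and probably a slip for 1.5 mg/dL

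*Combined protocol and SAP*

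**What the plan says.** Section 5.2.2 opens its list with "Participants with the following conditions will be ineligible", and one of the items is "Renal insufficiency, with creatinine greater than 1.5 mg/mL". Section 5.2 makes that list decide enrolment: "Those meeting inclusion criteria and no exclusion criteria may be enrolled into the study". Section 9.5 makes eligibility a reporting item, since the continuing renewal report is to carry "full trial data on: accrual and eligibility, protocol compliance" among other things.

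The creatinine limit appears only in Section 5.2.2. The Study Population entry in the Protocol Summary (Section 1) has no renal criterion, and the calendar in Section 6 (Table 3) lists no creatinine test that might show the limit in another unit.

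**The concern.** The unit looks wrong. A limit of 1.5 is workable for renal insufficiency if creatinine is in mg/dL. In mg/mL the same number is a concentration 100 times higher, and a rule set there would be expected never to apply. The document uses mg/mL correctly elsewhere, for ropivacaine strengths in Section 7.1.1, but here the unit belongs to a laboratory value that decides eligibility.

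What is at stake is whether the written criterion does its job. Read literally, it lets in women the investigators probably meant to keep out, and an auditor working from the text would have no ground to object. If staff quietly apply 1.5 mg/dL, which is the more likely case, practice departs from the approved protocol and a woman turned away at, say, 2 mg/dL meets no written exclusion. The estimand, the sample size and the analysis do not depend on this line.

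**Working it through.** **Inputs.** There is one figure from the documents: the limit of 1.5 mg/mL in Section 5.2.2. The conversion is 1 dL = 100 mL. The protocol does not derive the limit from anything else, so there is no calculation of its own to reproduce.

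**Step 1: the printed limit in mg/dL.**
1.5 mg/mL × 100 mL/dL = 150 mg/dL.

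**Step 2: the probable intent in the printed unit.**
1.5 mg/dL ÷ 100 mL/dL = 0.015 mg/mL.

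**Step 3: the ratio.**
150 ÷ 1.5 = 100. The printed limit is 100 times the probable one.

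**Step 4: where the two readings disagree.** Each reading excludes values strictly above its limit.

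| Creatinine | Limit as written (150 mg/dL) | Probable intent (1.5 mg/dL) |
|---|---|---|
| up to 1.5 mg/dL | not excluded | not excluded |
| above 1.5, up to 150 mg/dL | not excluded | excluded |
| above 150 mg/dL | excluded | excluded |

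For example, a woman at 3 mg/dL has 3 ÷ 100 = 0.03 mg/mL. That is twice the probable limit but only 0.03 ÷ 1.5 = 2% of the printed one, so the line as written does not exclude her.

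**Step 5: whom the written limit excludes.** This needs a figure the documents do not give, the highest blood creatinine a candidate could have. Call it C and try a range of illustrative values:

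| Assumed C (mg/dL) | C in mg/mL | Above 1.5 mg/mL? |
|---|---|---|
| 5 | 0.05 | no |
| 20 | 0.20 | no |
| 50 | 0.50 | no |
| 100 | 1.00 | no |
| 150 | 1.50 | no (equal, not above) |

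For any C up to 150 mg/dL the written criterion excludes nobody. The conclusion does not depend on which of these values is right.

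**Step 6: does other text correct it?** No. As set out above, the limit is stated once and is neither repeated nor converted elsewhere.

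**The case against.** The strongest reply is that this is a one-letter copy-edit with almost no consequence. The criterion begins by naming renal insufficiency, and a clinician will read the number accordingly. Section 5.2 says qualifying patients may be enrolled, so entry is permitted and not automatic. The calendar shows no step at which the literal number would be applied mechanically. Section 7.1.6 describes ropivacaine as cleared mainly by the liver, with renal clearance of 1 mL/min against a total plasma clearance of about 440 mL/min (1 ÷ 440 = 0.2%). So the documents give no basis for claiming a material hazard from one dose. Most of this stands, and it is why the point is minor. It is not a full answer, because the sentence ties the exclusion to the number: renal insufficiency counts only when creatinine exceeds the stated limit. The clearance figures do not prove safety either, since the same section says 86% of a dose leaves in the urine, mostly as metabolites.

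Three further objections deserve a reply.

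- **The intended unit is an inference.** This stands. The documents prove the conversion but not the intent, which is why the finding says probably and the fix starts with confirmation.
- **The text was read by machine, so the letter could be a misreading.** This cannot be excluded outright. But the line is otherwise intact, and concentration units are rendered sensibly elsewhere. Nothing suggests a misreading here.
- **The gap between the two limits, 150 − 1.5 = 148.5 mg/dL, exaggerates the problem.** This stands. If nobody approaches 150 mg/dL, the upper part of that band is empty and its width says nothing about patients. The group that matters is candidates somewhat above 1.5 mg/dL, and its size is unknown.

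**Conclusion.** The concern holds as a minor error. The renal exclusion as printed is 150 mg/dL, a factor of 100 above the probable intent, in a line that governs enrolment and is not corrected elsewhere. The conversion is certain.

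Two statements rest on assumptions. That mg/dL was meant is an inference from the number and from the criterion's evident purpose. That the written limit excludes nobody assumes that creatinine refers to blood and that no candidate exceeds 150 mg/dL.

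The number of women affected cannot be stated from the documents and is probably small. No added risk to patients is claimed. No calculation in the protocol is wrong, and sample size, power and alpha are unaffected.

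**What to change.** Ask the investigator to confirm the intended unit. If it is mg/dL, reword the item in Section 5.2.2 as *renal insufficiency, with serum creatinine greater than 1.5 mg/dL*. The unit is the correction. Adding the word serum is a clarification the documents do not themselves supply, so the investigator should confirm that as well.

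The cost is one unit and one word. Section 8.1 requires IRB approval before any protocol change is put into effect, so the edit should travel with the next amendment; it does not justify one of its own. Staff should also be asked which limit they have been applying. A retrospective eligibility check is needed only if the answer is the literal one.

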5.3 Inclusion of Women and Minorities

This study is open to accrual of women only. Individuals of all races and ethnic groups are eligible for this trial. There is no bias towards age or race in the clinical trial outlined.

5.4 Determination of Eligibility

Potential subjects will be consented by the study investigators or study staff. If determined eligible, subjects will be registered with the study coordinator through the assignment of a study-specific ID number.

5.5 Randomization

During the study, patients desiring a bilateral mastectomy followed by bilateral immediate tissue expander reconstruction will be randomized to ropivacaine- pre-operatively placed paravertebral blocks or subcutaneous paravertebral saline (placebo) injections at the same site as the paravertebral block. Randomization will be performed by the pharmacy when the medication is requested prior to paravertebral block administration.

A master list of randomization assignments made by the protocol biostatistician will be delivered to the Research Pharmacy at Johns Hopkins. Other key personnel may also receive this list, if required.

5.6 Blinding

Both patients and the treating anesthesiologist(s) will be blinded as to whether the patients are receiving a ropivacaine (treatment) or saline (placebo) solution through the Day 90 visit. One anesthesiologist (who is also a co-investigator), which will not be involved with the intra- and postoperative patient care and data collection, will perform all the paravertebral blocks and sham procedures. The anesthesiologists managing intra- and postoperative patient care and all data collection will be unaware of the group assignment. Postoperative assessments will be performed by anesthesiologists who will be blinded to each patient's group. This strategy will allow a double-blinded design. Blinding the study will help to reduce the chance of bias in subjective outcomes such as pain scores and quality-of-life scores. Once all enrolled patients have completed their Day 90 visit, unblinding will occur for study staff to enable data analysis. Patients will have the option of learning their treatment assignment group once they have completed their Year 4 follow-up interview.

In case of an emergency when the treating investigator deems identification of the study drug necessary for the purpose of providing urgent patient care, and knowledge of the subject's treatment assignment will alter subsequent care, then the investigator is authorized to break the blind. In order to learn of the randomization assignment, the Principal Investigator or designee will contact the Research Pharmacy to request treatment assignment information.

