5.1 Summary of Study Design

Participants meeting inclusion criteria will be enrolled and baseline data collection completed prior to randomization and surgery. Baseline data collection includes a general patient history, the Patient Pain Assessment Questionnaire which includes static and moving pain scores as well as nausea and sleep interference scores (Appendix A), the Subjective Pain Survey (Appendix B), the pre-operative Breast-Q (Appendix C), the RAND-36 (Appendix E), and the Quick DASH survey (Appendix F).

Patients will be randomized 1:1 to ropivacaine- (treatment) pre-operatively placed paravertebral blocks or subcutaneous paravertebral saline (placebo) injections in a double-blinded design. Neither the treatment team (the anesthesiologist and the surgeon) nor the patient will know the randomization assignment. The pharmacy will be unmasked.

Patient-specific surgical details will be recorded intraoperatively. Following the surgery, post-operative pain [(measured by the Patient Pain Assessment Questionnaire (Appendix A)], pain medication/opioid use, and the occurrence of adverse events (AEs)/serious adverse events (SAEs) will be assessed routinely by staff during the hospital stay and on Days 2 and 3 by telephone interview with study staff for discharged patients. The typical post-operative length of hospital stay is approximately one day. Participants are to return to clinic for the Day 7 (± 2 days) follow-up visit. At this visit an updated medical history will be completed, pain medication/opioid use recorded, and participant AEs/SAEs assessed. Additionally, participants will complete the following questionnaires: Patient Pain Assessment, RAND-36, and Quick DASH.

Long-term quality-of-life/health outcomes assessments will be done on post-operative Day 90 (± 14 days), Year 2 (± 14 days), and Year 4 (± 14 days). During the Day 90 visit, pain scores (Patient Pain Assessment Questionnaire), pain medication/opioid use, post-operative Breast-Q, RAND-36, and the Quick DASH will be administered. The Year 2 and Year 4 follow-ups are included as tertiary endpoints to capture differences in chronic pain, and patients will be asked to complete the same questionnaires as at the Day 90 follow up.

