5.11 Duration of Study Participation

Study participation continues through Year 4 post-operatively. However, the majority of data collection will occur during the first 7 days after the participant’s immediate tissue expander reconstruction following mastectomy. An additional study visit will occur in clinic at Day 90 (± 14 days), prior to the participant’s undergoing any additional reconstructive breast surgery procedures. Thereafter, follow-up phone interviews will occur at post-operative Year 2 (± 14 days), and post-operative Year 4 (± 14 days).

Participants are to return to clinic for a Day 90 (± 14 days) follow-up visit. To encourage participation, participant parking and a \$15 gift card will be given (or mailed) to participants who complete the Day 90 visit.

If a participant chooses to withdraw, is withdrawn, or refuses to participate through Day 90, all efforts will be made to collect all Day 90 post-operative data at the time of study withdrawal. Reasons for premature participation/treatment withdrawal will be recorded to the best of the study team’s ability. Reasons for early withdrawal may include the following:

1. Unanticipated or serious adverse events.
2. Inter-current illness that prevents further administration of treatment or would affect assessment of clinical status to a significant degree.
3. Subject becomes pregnant.
4. Subject refuses to continue treatment.
5. Any reason the study physician deems it necessary for the benefit of the participant.
6. Subject is lost to follow-up.

6. Study Calendar

Table 3. Calendar of study events/procedures.

Parameter	Pre-Study	Surgery (Day 0)	Day1	Day 2*	Day 3*	Day 7 (± 2 days)	Day 90 (± 14 days)	Post-Op Years 2 & 4 (± 14 days)
General Patient History Form	X							
Update Medical History		X	X			X	X	X
Treatment administration (Ropivacaine/Placebo)		X						
Intra-Operative Case report Form (CRF)		X						
Adverse Events of Interest/SAE Assessment		X	X	X	X	X	X	
Pain Meds/Opioid Use	X		X	X	X	X	X	
Questionnaires								
Patient Pain Assessment Questionnaire	X		X	X	X	X	X	X

Subjective Pain Survey	X							
BREAST-Q [®] , Pre-Op	X							
BREAST-Q [®] , Post-Op							X	X
RAND-36 Questionnaire	X					X	X	X
Quick DASH Questionnaire	X					X	X	X

Note: Additional tests may be performed at the discretion of the treating investigator as clinically indicated.

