9.6 Data Management

All information will be collected on study-specific case report forms (CRFs) by study staff. The Principal Investigator as well as the Sidney Kimmel Comprehensive Cancer Center Clinical Research Office will review these data for completeness and accuracy.

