10.1.3 Tertiary Objectives

To determine if long-term changes in Quality of Life scores [the RAND-36 Health Survey, Disability of the Arm, Shoulder, and Hand (Quick DASH) questionnaire, and Breast-Q scores] differ between women undergoing bilateral mastectomy followed by bilateral immediate tissue expander reconstruction randomized either to ropivacaine- (treatment) pre-operatively placed paravertebral blocks or subcutaneous paravertebral saline (placebo) injections.

This data will be collected via validated questionnaires through patient interviews at 3-months, 2-years, and 4-years (± 14 days) after surgery.

Once enrolled in the study, participants will be encouraged to remain in the study for the 4 years following surgery in order to get final pain scores and quality-of-life/health outcome survey information. Participants who cannot be contacted after several phone attempts and the sending of 2 certified letters via US Postal Service for 3-month, 2-year, and/or 4-year outcome assessments will be considered lost to follow-up.

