10.2 Study Design

Descriptive statistics for all outcome data (primary, secondary, and tertiary) will be calculated for each treatment group (ropivacaine or placebo), for each time point (days 1-3, day 90, year 2 and year 4). Student's t-test or Wilcoxon rank sum test will be used to compare the 2 treatment groups with regards to continuous or ordinal (approximately continuous) data, based on the distribution of the values (normally distributed or not normally distributed). Also change from baseline to each time point (follow-up) will be calculated for each outcome. The distributions of these "change values" will be analyzed in the same manner (depending on distribution). P-values less than 0.05 will be considered statistically significant for the primary outcome.

Longitudinal methods will be used to examine trends in scores, and changes in scores over time.

Opioid use also will be analyzed. IV morphine delivered via a Patient Controlled Analgesia pump during the first 24 hours of post-operative hospitalization will be recorded. Oxycodone and Tylenol taken by the patient after the first 24 hours until post-operative day seven will be recorded by the patient unless the patient is still hospitalized, in which case it will be recorded in the patient's medical record and abstracted by study staff. Answers to pain questionnaires and information regarding analgesic use will be verified by daily telephone calls to the patients by study staff. A common "pain unit" will be developed to standardize the various methods of opioid administration. Survival analyses will be used to compare time to opioid use, and time to stopping of opioid use. Descriptive statistics will be used to quantify amount and timing of opioid use, as well as proportion of patients requiring opioids post-operatively.

Furthermore, we will use the DASH survey, BREAST-Q[®], and the RAND-36 to determine the amount of functional long-term differences (3 months, 2 and 4 years after surgery) between treatment groups. These surveys will be used to compare the functional use of the arm before surgery to its use three months after mastectomy with immediate reconstruction.

Adverse events will be quantified and proportions of patients in each treatment group with different specific types of adverse events will be compared for safety data. Chi Square tests or Fisher's Exact Tests will be used to compare the proportions of patients with adverse events.

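### Section 5.6 unblinds study staff after the last Day 90 visit and does not keep those who will conduct the Year 2 and Year 4 interviews blinded

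*Combined protocol and SAP*

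**What the plan says.** Section 5.6 sets the date and the recipients of the release: "Once all enrolled patients have completed their Day 90 visit, unblinding will occur for study staff to enable data analysis". It gives a reason for masking in the same section: "Blinding the study will help to reduce the chance of bias in subjective outcomes such as pain scores and quality-of-life scores". Patients may learn their own assignment only after their own Year 4 interview.

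The recipients are named as study staff, without subdivision. The protocol uses that term for people in contact with patients and data:

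- Section 5.1 has early outcomes assessed "on Days 2 and 3 by telephone interview with study staff for discharged patients".
- Section 10.2: "Answers to pain questionnaires and information regarding analgesic use will be verified by daily telephone calls to the patients by study staff".
- Section 9.6: "All information will be collected on study-specific case report forms (CRFs) by study staff".

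Section 5.11 makes the Year 2 and Year 4 follow-ups telephone interviews. Section 10.1.3 says of the tertiary quality-of-life outcomes: "This data will be collected via validated questionnaires through patient interviews at 3-months, 2-years, and 4-years (± 14 days) after surgery". The study calendar (Table 3) lists the Patient Pain Assessment Questionnaire, RAND-36, Quick DASH and post-operative BREAST-Q at both times. Section 5.1 calls these follow-ups tertiary endpoints meant to capture differences in chronic pain.

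**The concern.** The long-term comparison rests on subjective scores obtained by telephone after the codes have been released to a group that, in this protocol's vocabulary, includes those who make such calls. Pain and quality of life are the outcomes that Section 5.6 says blinding is there to protect. If the caller knows the arm, that protection is lost at the interviewer. The wording of prompts could be affected. So could the effort made to reach a patient, because Section 10.1.3 does not fix the number of phone attempts before someone counts as lost to follow-up. Both routes are inferences; the documents report neither.

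The breadth of the release gains nothing. Its stated purpose is data analysis, and for that only the analysts need the codes.

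**Working it through.** The plan gives no figure on this point to reproduce. The check has two parts: whether any text keeps the late interviewers blinded, and how many interviews fall after the release.

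**1. Is there an exemption?**

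- *Section 5.6, anesthesiologists.* Those managing intra- and postoperative care and data collection, and those doing postoperative assessments, are to be unaware of the assignment. These sentences have no end date and do not mention the Year 2 or Year 4 calls. The section's opening sentence runs the blinding of patients and treating anesthesiologists to Day 90.
- *Section 5.7.* Blinding of physicians and the study team is to be maintained unless medical care requires otherwise. This sits under treatment administration, has no end date, and is not reconciled with the dated release in 5.6.
- *Terms.* The calendar footnote assigns the Day 2 and Day 3 calls to a study team member, while Section 5.1 assigns the same calls to study staff. The two terms are used interchangeably, so 5.7 does not define a separate, protected group of callers.
- *Sections 5.11 and 10.1.3.* Neither names who conducts the Year 2 and Year 4 interviews. That they are study staff is inferred, chiefly from 9.6.

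No sentence limits the release to analysts or keeps the late interviewers masked.

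**2. How many interviews follow the release?**

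Inputs: 70 patients (10.3); visit windows of ±14 days (5.1); all Day 90 data by month 24 (10.3), or two-year accrual (synopsis), which puts the last Day 90 visit about three months later. Assumptions: even accrual, no dropout, one month = 30.44 days. So Day 90 = 90/30.44 = 2.96 months and 14 days = 0.46 months.

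Let A be the accrual period, U the month of unblinding, and Y2 the time from surgery to the Year 2 call (24 ± 0.46), all in months. The share of Year 2 calls made before unblinding is max(0, U − Y2)/A. Under 10.3, A = 24 − 2.96 = 21.04. Otherwise U = A + 2.96 ± 0.46.

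| Case | A | U | Y2 | Before unblinding | After, of 70 |
|---|---|---|---|---|---|
| 10.3, nominal | 21.04 | 24.00 | 24.00 | 0 | 70 (100%) |
| 10.3, early calls | 21.04 | 24.00 | 23.54 | 0.46/21.04 = 2.2% | 68.5 (97.8%) |
| 10.3, early calls and last Day 90 visit 14 days late | 21.04 | 24.46 | 23.54 | 0.92/21.04 = 4.4% | 66.9 (95.6%) |
| Two-year accrual, nominal | 24 | 26.96 | 24.00 | 2.96/24 = 12.3% | 61.4 (87.7%) |
| Two-year, late release and early calls | 24 | 27.42 | 23.54 | 3.88/24 = 16.2% | 58.7 (83.8%) |
| Two-year, early release and late calls | 24 | 26.50 | 24.46 | 2.04/24 = 8.5% | 64.1 (91.5%) |

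Sensitivity to assumptions that are not in the documents:

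- *Uneven two-year accrual*, with t = (U − Y2)/A. If the starting rate is twice the final rate, the share before is 4t/3 − t²/3; at t = 3.88/24 this leaves 55.5 after (79.3%), the lowest value. If the starting rate is half the final rate, it is 2t/3 + t²/3; at t = 2.04/24 this leaves 65.9 after (94.1%), the highest.
- *Accrual of 30 months, even.* 8.04/30 to 9.88/30 before, leaving 51.2 to 47.0 after (73.2% to 67.1%).
- *Accrual of 36 months, even.* 14.04/36 to 15.88/36 before, leaving 42.7 to 39.1 after (61.0% to 55.9%).

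Year 4: the first call is at month 48. It precedes unblinding only if A + 2.96 > 48, that is A > 45.0. With an early call and a late last Day 90 visit the condition is A + 3.42 > 47.54, that is A > 44.1. On the document's own timetables the first Year 4 call comes about 20 to 24 months after the release.

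**The case against.** The best reply is that this is an ambiguity and not a stated plan to use unblinded callers. The release is tied to data analysis, so a reader may take it as meant for analysis personnel, and no section names the late interviewers. Section 5.7 says that study-team blinding is maintained. The rater is the patient, whose option to learn her arm is deferred until after her own Year 4 interview, which suggests that the plan means to protect these scores at their source. The scales are fixed, and Section 5.1 says "patients will be asked to complete the same questionnaires as at the Day 90 follow up", which leaves open how far staff ask the questions or record the answers. The outcomes are tertiary.

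Much of this stands as a limit. The text permits unblinded callers without requiring them, the influence of an interviewer cannot be sized, and patient masking reduces what is at risk. It does not remove the point. A stated purpose does not restrict who receives the codes, and the undated sentence in 5.7 conflicts with the dated release in 5.6 if it is read as covering Years 2 to 4. If the intention is analysts only, the amendment merely says so.

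A further objection is that Section 5.5 lets other key personnel receive the randomization list if required, so editing 5.6 leaves that route open. A clause that keeps the interviewers themselves blinded holds whatever the route.

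**Conclusion.** The concern holds. Section 5.6 releases assignments to study staff as a whole once the last Day 90 visit is done, and nothing in the document keeps the Year 2 and Year 4 interviewers masked.

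On the document's own timetables, 84% to 100% of Year 2 interviews and all Year 4 interviews come after the release, given even accrual and no dropout. Slower accrual lowers the Year 2 share, but it is still more than half at 36 months. These are interviews exposed if the callers hold the codes; they are not an estimate of bias. The weakest link is the inference that study staff make the late calls.

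Only the long-term tertiary outcomes are at issue. The 6-hour primary endpoint and all data through Day 90 are untouched by this release. The change is worth making because it is cheap, and because masking cannot be restored to staff who have already seen the codes.

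**What to change.** In Section 5.6, replace the release sentence with:

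> Once all enrolled patients have completed their Day 90 visit, assignments will be released only to the statistician and those who need them for the analysis; staff who conduct or record the Year 2 and Year 4 interviews remain blinded to individual assignments until the last Year 4 interview.

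This also fits the study-team blinding statement in 5.7, which should refer to it so that the two sections agree.

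The cost is one sentence, with no new visit, assessment or committee. An investigator who needs the codes for the analysis can still have them. There are three downsides: some site staff learn individual assignments later; no one holding the codes may make the Year 2 or Year 4 calls; and a patient who asks for her assignment after her own Year 4 interview must be told by a code holder and not by the caller. The documents give no staffing numbers, so this burden cannot be sized.
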